Appendix IV – Mayo Patient Survey

List of Abbreviations

3DCRT	3-D Conformal Radiation Therapy
AE	Adverse Event/Adverse Experience
CBCT	Cone Beam CT
CFR	Code of Federal Regulations
CRF	Case Report Form
CTV	Clinical Target Volume
DSMB	Data and Safety Monitoring Board
FDA	Food and Drug Administration
GCP	Good Clinical Practice
HIPAA	Health Insurance Portability and Accountability Act
IBTR	Ipsilateral breast tumor recurrence
IMRT	Intensity Modulated Radiation Therapy
IRB	Institutional Review Board
MRI	Magnetic Resonance Imaging
PHI	Protected Health Information
PI	Principal Investigator
PTV	Planning Target Volume
QOL	Quality of Life
RBE	Relative biologic effectiveness
RT	Radiation Therapy
SAE	Serious Adverse Event/Serious Adverse Experience
SOP	Standard Operating Procedure
XRT	X-ray Radiation Therapy

SCHEMA

N=25 patients

Study Design: This is a phase II trial to determine the effect of 25Gy in 5 fractions to the whole breast alone before breast conserving surgery.

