7.11 Surgery

7.11.1 Surgical treatment will be done at the discretion of the treating surgeon.
7.11.2 Surgery will be done at 8 weeks after the completion of radiation.
Acceptable range is 4-16 weeks after.

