- *Cause specific survival*: is defined as the time from registration to death due to breast cancer. If the cause of death is unknown or difficult to establish, patients with a distant failure at the time of death would be censored as dying from breast cancer
- *Overall survival*: is defined as the time from registration to death due to any cause.

16.3 Exploratory endpoints:

16.31 Patient self-reported cosmesis, i.e. fatigue, breast pain, and other patient reported outcomes.

16.32 Clinical features, treatment technique, dose-volume parameters, histologic and genetic variants associated with adverse events, and fair and poor cosmetic outcomes or unplanned surgical intervention.

16.33 Tumor mutation signatures before and after radiation; correlate tumor mutation signatures before and after radiation with pathologic information at the time of surgery.

16.34 Pathologic changes seen in breast cancer patients with preoperative radiation.

The following definitions are used for the exploratory endpoints of interest:

- *Patient Reported Outcomes/Quality of life:* Elements of the Patient-Reported Outcomes Version of the Common Terminology Criteria for Adverse Events (PRO-CTCAE) will be used for patient self-reporting of toxicities. The Breast Cancer Treatment Outcomes Scale (BCTOS) will be used to measure patient reported functional status (pain, mobility). Other measures of fatigue, pain, and arm function are listed in the appendix.

- *Provider reported cosmetic outcomes*: the physician or mid-level reported outcome will be assessed using the Harvard Cosmesis Scale baseline, EOT, 3 months, 12 months, and yearly after.
- *Patient self-reported cosmetic outcomes*: the patient self-reported outcome will be assessed using a modified Harvard Cosmesis Scale and the BCTOS at baseline, 2 years, and 5 years.
- *Panel assessed cosmetic outcome*: in addition to patient self-reported and physician reported outcomes, cosmesis will be assessed by a panel of breast cancer medical providers using digital photographs from baseline and at 2 years.

16.4 Statistical Design:

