- 16.531 *Quality of life:* The subscales of the BCTOS, elements from CTCAE-PRO, and other patient reported measures such as fatigue, breast pain, breast shape, and arm related morbidity outlined in the appendix will be summarized as the mean \pm SD and median (minimum value, maximum value). Scale score trajectories over time will be examined using stream plots and mean plots with standard deviation error bars overall. Analysis will include percent change from baseline using t-tests and generalized linear models to test for changes at each time point and non-zero slope respectfully.
- 16.532 *Cosmesis:* The values of the cosmesis instruments (patient self-reported and panel-assessed) will be summarized with the frequencies and confidence intervals of fair or poor cosmesis events at baseline, 2 years, and 5 years.
- 16.533 Tumor mutation signatures will be analyzed before and after radiotherapy as compared to pathologic information at the time of surgery. Continuous variable will be compared using unpaired t tests and monimal variables will be compared using contingency tables and Chi square analyses.
- 16.534 Pathologic changes due to preoperative radiotherapy observed at the time of definitive surgery will be described.

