Blistering of the treated breast or chest wall; *response options 0 to 10, 0 = not at all, 10 = blistering as much as could be*

Itching of the treated breast or chest wall; *response options 0 to 10, 0 = not at all, 10 = as itchy as it could be*

Skin burns from radiation on your back; *response options 0 to 10, 0 = not at all, 10 = as itchy as it could be*

11. If you had to do it all over again, would you have this **RADIATION** treatment again?

Yes
No

12. Have you been diagnosed with an infection at your breast cancer surgical site that required treatment with antibiotics or surgery?

Yes
 No

We are interested in your evaluation of your physical appearance and functioning. Please rate the following items from 0 to 10, according to how you feel **AT THIS POINT IN TIME**.

Is the color of your treated breast/chest wall skin different than the other side (red, tan, or lighter)? *response options 0 to 10, 0 = not at all, 10 = as different as it could be*

Do you have visible small blood vessels (spider veins) on your treated breast/chest wall?
response options 0 to 10, 0 = not at all, 10 = as many as it could be

Do you have pain with swallowing? *response options 0 to 10, 0 = not at all, 10 = as painful as could be*

Do you have numbness or a tingling sensation in the arm on the side that was treated?
response options 0 to 10, 0 = not at all, 10 = as much as it could be

Do you have tightness, pulling, or stretching in the arm, breast, or chest area (in the side that was treated?) *response options 0 to 10, 0 = not at all, 10 = as much as it could be*

Do you have tenderness or discomfort on the treated breast/chest wall? *response options 0 to 10, 0 = not at all, 10 = as much as it could be*

Overall, how would you rate the cosmetic results of your breast treatment?
 Excellent Good Fair Poor

Please rate the following items according to your evaluation **at this point in time**:

Breast/chest wall texture (hardening)	 None	 Slight	 Moderate	 Large
Arm heaviness	 None	 Slight	 Moderate	 Large
Shoulder movement	 None	 Slight	 Moderate	 Large

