Arm movement	 None	 Slight	 Moderate	 Large
Breast/chest wall pain	 None	 Slight	 Moderate	 Large
Ability to lift objects	 None	 Slight	 Moderate	 Large
Fit of shirt sleeve	 None	 Slight	 Moderate	 Large
Breast/chest wall tenderness	 None	 Slight	 Moderate	 Large
Shoulder stiffness	 None	 Slight	 Moderate	 Large
Scar tissue	 None	 Slight	 Moderate	 Large
Shoulder pain	 None	 Slight	 Moderate	 Large
Arm pain	 None	 Slight	 Moderate	 Large
Arm swelling	 None	 Slight	 Moderate	 Large
Breast/chest wall swelling	 None	 Slight	 Moderate	 Large
Arm stiffness	 None	 Slight	 Moderate	 Large
Breast/chest wall sensitivity	 None	 Slight	 Moderate	 Large
Fit of clothing	 None	 Slight	 Moderate	 Large
Axillary (arm pit) fullness or numbness	 None	 Slight	 Moderate	 Large

Please complete the following questions if you had breast conserving therapy or mastectomy with reconstruction.

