Please rate the following items according to your evaluation **at this point in time**

Breast size	 None	 Slight	 Moderate	 Large
Nipple appearance	 None	 Slight	 Moderate	 Large
Breast shape	 None	 Slight	 Moderate	 Large
Breast elevation (how high the breast is)	 None	 Slight	 Moderate	 Large
Fit of bra	 None	 Slight	 Moderate	 Large
Breast heaviness	 None	 Slight	 Moderate	 Large

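### Appendix II tells patients to skip six breast-appearance items unless breast-conserving therapy or reconstruction has already taken place, so read literally these items, including breast shape, have no baseline

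*Combined protocol and SAP*

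**What the plan says.** The Schema describes "25Gy in 5 fractions to the whole breast alone before breast conserving surgery". Section 7.11 adds: "Surgery will be done at 8 weeks after the completion of radiation", with 4 to 16 weeks acceptable. Section 1.0 defines breast-conserving therapy as surgery together with radiation.

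Section 16.3 states that patient self-reported cosmesis "will be assessed using a modified Harvard Cosmesis Scale and the BCTOS at baseline, 2 years, and 5 years". Section 16.531 covers the BCTOS subscales and further patient-reported measures from the appendix, breast shape among them, and plans percent change from baseline with t-tests and generalized linear models. Section 16.532 summarises "fair or poor cosmesis events at baseline, 2 years, and 5 years".

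In Appendix II, six items rated None to Large follow the instruction "Please complete the following questions if you had breast conserving therapy or mastectomy with reconstruction". Before that instruction stands the question "Overall, how would you rate the cosmetic results of your breast treatment", answered Excellent, Good, Fair or Poor. Question 10 of the same survey contains "Skin burns from radiation on your back; *response options 0 to 10, 0 = not at all, 10 = as itchy as it could be".

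**The concern.** The survey is worded for women who have already been operated on. A patient who fills it in before radiation and obeys the skip line leaves all six items blank. The plan then lacks the baseline for a variable that it names for a change-from-baseline analysis, and a baseline that was never recorded cannot be recovered once treatment has begun.

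Two smaller wording problems sit in the same form. The overall rating asks about the results of treatment, which has no clear meaning before any treatment, although a baseline fair/poor frequency is planned. The upper anchor of the back skin-burn item describes itching.

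**Working it through.** The plan gives no figure on this point, so there is none to reproduce. The check sets the form against the treatment sequence and the analysis plan, then counts.

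**1. Can anyone meet the condition at baseline?**
- The condition is in the past tense and requires breast-conserving therapy, or mastectomy with reconstruction (Appendix II).
- Breast-conserving therapy is surgery plus radiation (Section 1.0). Prior radiation to the ipsilateral breast and recurrent breast cancer are exclusions (Sections 3.2.7 and 3.2.8), and surgery is still planned at entry (Section 3.1.8).
- So no eligible patient has had breast-conserving therapy of the study breast at baseline.

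**2. Is a baseline needed for these items?**
- Section 16.531 names breast shape among the appendix measures. In the visible text a breast-shape item occurs only behind the skip line.
- Section 16.3 schedules the BCTOS at baseline, 2 years and 5 years. The documents do not say which Appendix II items form which BCTOS subscale, so the effect on a subscale is conditional: it applies to any subscale built from these six items.

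**3. How many pairs remain?**
Let N be the number surveyed and f the share who answer at baseline despite the instruction. Pairs available = N × f, assuming complete follow-up. N is 25 at maximum accrual or 22 evaluable (Section 16.42). The documents give no value for f, so a range is shown:

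| f (assumed) | N = 25 | N = 22 |
|---|---|---|
| 0 (instruction followed) | 0 | 0 |
| 0.25 | 6.25, about 6 | 5.5 |
| 0.50 | 12.5, so 12 or 13 | 11 |
| 1 | 25 | 22 |

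For f between 0 and 1, those who answer have selected themselves.

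**4. Which other visits fall before surgery?**
Surgery at 4 to 16 weeks is day 4 × 7 = 28 to day 16 × 7 = 112 after radiation, with the target at 8 × 7 = 56. Visit windows are from the footnotes to Section 18.1, counted from the end of radiation with a month taken as 30 days:
- End of treatment, and Day 15 (15 ± 3 = days 12 to 18): before surgery for all.
- D90 (90 ± 30 = days 60 to 120): mixed.
- D180 (180 ± 60 = days 120 to 240) and later: after surgery for all.

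Section 16.3 asks for patient-rated cosmesis only at baseline, 2 years and 5 years, so baseline is the visit that counts. Section 18.1 lists a breast radiotherapy questionnaire at end of treatment and in the observation phase, but the visible text does not show whether that is the Appendix II form.

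**5. What is not behind the skip line?**
Eighteen other None-to-Large items (texture, scar tissue, swelling, pain, arm and shoulder items among them), the 0 to 10 items on skin colour and visible vessels, and the overall Excellent-to-Poor rating. The skip line therefore governs 6 of 6 + 18 = 24 None-to-Large items.

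**6. The anchor.**
Question 10 has five severity items. Flaking, bleeding, blistering and itching each end on their own symptom. The back-burn item repeats the itching anchor, so 1 of 5 is miscopied.

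**The case against.** The case against giving this much weight is strong on scope, and most of it stands.

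- A reader might infer that change from baseline is lost for patient-reported outcomes generally. It is not: most items are unaffected, including the pain and mobility items for which Section 16.3 says the BCTOS measures function.
- A reader might infer that no baseline fair/poor frequency can exist. The only patient item on that scale stands before the skip line, so it is awkward at baseline but not skipped. Section 16.532 also uses panel assessment, which Section 16.3 bases on photographs at baseline and 2 years.
- A reader might infer that the effect of radiation on the intact breast goes unobserved. Section 16.3 schedules provider-rated cosmesis at baseline, end of treatment and 3 months, and Section 10.4 grades dermatitis, pigmentation, fibrosis and pain at baseline and each evaluation.
- A reader might count end of treatment, Day 15 and D90 as lost cosmesis assessments. Section 16.3 does not require patient-rated cosmesis then.
- Blank answers are a prediction. By pairing breast-conserving therapy with reconstruction, the line was plausibly meant to screen out women with no breast to rate, and some patients may answer anyway. After radiation and before surgery the wording is ambiguous.
- The Section 4.0 table and part of the appendices are not visible, so a separate baseline form cannot be ruled out.

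The objection does not remove the conflict at baseline. There the condition is unmet for every patient, the visible text contains no override, and the plan names breast shape for change from baseline. An intention to screen out only women without a breast is a reason to say so on the form. The anchor error is a copying slip. The question stem still asks about severity and no analysis names the item, so it does not make the answers meaningless.

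**Conclusion.** The point holds in a narrow form. Read literally, Appendix II leaves six appearance items blank at baseline, and Section 16.531 needs a baseline for at least one of them. The loss is complete (0 of up to 25 patients with a pair) if the instruction is followed, and partial and self-selected if it is followed by some.

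This rests on three assumptions: patients take the instruction at its word, the Appendix II form is the one used at baseline, and no pre-surgery version exists outside the visible text. Effects on BCTOS subscales depend further on an item-to-subscale mapping that the documents do not give.

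The overall cosmesis rating is answerable but unclear before treatment, and one anchor needs correction. The affected analyses are exploratory. Provider and panel cosmesis and the pCR endpoint are unaffected. Minor priority, worth settling before further baselines are collected.

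**What to change.** 1. In Appendix II, for baseline and any other administration before surgery, replace the skip line with one that asks every patient with an intact breast to answer the six items, for example: *Please complete for the breast with cancer.* Leave the item wording unchanged.
2. At baseline, word the overall question as the current appearance of that breast compared with the other.
3. Give the back skin-burn item an upper anchor that describes burns.
4. In Section 16.531, state that patients already surveyed without baseline answers are reported as missing at baseline and left out of change from baseline on these items. Do not use answers given after radiation and before surgery as the reference: they already contain the radiation effect, and they may be blank for the same reason.

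The cost is one IRB-approved form version, with no extra visit or staff. The pre-surgery form will differ slightly from the survey used in routine care (Section 11.4). The overall rating at baseline will also come from a differently worded question than the later ratings, so the baseline fair/poor frequency should be presented as descriptive.

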Appendix III
Mayo Patient Survey PRO-CTCAE Mayo 10

Survey Date (mm/dd/yyyy):

Please answer the following questions about your symptoms.

	Not at all	A little bit	Somewhat	Quite a bit	Very much
In the last 7 days, how much did anxiety INTERFERE with your usual or daily activities:					
In the last 7 days, how much did insomnia including difficulty falling asleep, staying asleep, or waking up early INTERFERE with your usual or daily activities:					
In the last 7 days, how much did decreased appetite INTERFERE with your usual or daily activities:					
	Never	Rarely	Occasionally	Frequently	Almost Constantly
In the last 7 days, how OFTEN did you have nausea:					
	Not at all	A little bit	Somewhat	Quite a bit	Very much
In the last 7 days, how much did shortness of breath INTERFERE with your usual or daily activities:					
In the last 7 days, how much did problems with concentration INTERFERE with your usual or daily activities:					
In the last 7 days, how much did sad or unhappy feelings INTERFERE with your usual or daily activities:					
	None	Mild	Moderate	Quite a bit	Very severe
In the last 7 days, what was the SEVERITY of your constipation at its WORST:					
	Not at all	A little bit	Somewhat	Quite a bit	Very much
In the last 7 days, how much did numbness or tingling in your hands or feet INTERFERE with your usual or daily activities:					
	Never	Rarely	Occasionally	Frequently	Almost Constantly
In the last 7 days, how OFTEN did you have loose or watery stools (diarrhea):					

Appendix IV

Mayo Patient Survey

Survey Date (mm/dd/yyyy):

Please respond to each item by choosing one number per row.
